**Figure 1. Flow diagram**

*Anticipated plot design, illustrating potential reasons for exclusion:*

**Table 1. Baseline characteristics in the intention-to-treat population**

Characteristics	Heated mittens (n = )	Sham mittens (n = )	Total (n=)
Demographics			
Age, years			
Females, n (%)			
Height, m			
Weight, kg			
Body Mass Index, kg/m 			
Disease duration, years			
Stratification factor			
CMC-1 OA, n (%)			
AUSCAN scores			
Physical function a , 0-900 score			
Pain, 0-500 score			
Stiffness, 0-100 score			
Clinical assessments			
Tender joint count, 0-30			
Swollen joint count, 0-30			
Number of CMC-1 dislocations, 0-2			
Visual analog scales, 0-100			
Hand pain			
Global rating of hand OA related problems			
Performance measure			
Grip strength right hand, N			
Grip strength left hand, N			
Analgesics			
Analgesic user, n (%)			

Values are mean (SD) unless otherwise stated in the table.

CMC-1 OA, first carpometacarpal osteoarthritis; AUSCAN, Australian/Canadian Osteoarthritis Hand Index.

aPrimary outcome measure.

*Further statistical information related to table 1:*

Data will be presented as mean with standard deviation (SD) when normally distributed or as median with interquartile range in case of skewed data. Dichotomous and categorical data will be presented in proportions. Normality of the data will be assessed using Q-Q plots, and histograms.

**Table 2. Change from baseline in primary and secondary outcomes at week 7 in the ITT population**

	Heated mittens (n = )	Sham mittens (n = )	Difference between groups (95% CI)	P-value
Primary outcome				
AUSCAN physical function, 0-900 score				
Key secondary outcomes				
AUSCAN pain, 0-500 score				
Global rating of hand OA related problems, 0-100 VAS score				
Grip strength right hand, N				
Grip strength left hand, N				
Other secondary outcomes				
AUSCAN stiffness, 0-100 score				-
Tender joint count, 0-30				-
Swollen joint count, 0-30				-
Hand pain, 0-100 VAS score				-
Analgesics discontinued, n(%)				-

Values are least squares means (standard error) unless otherwise stated in the table.

95%CI, 95% confidence interval; AUSCAN, Australian/Canadian Osteoarthritis Hand Index; ITT, intention-to-treat; VAS, visual analog scale. N, Newtons.

*Further statistical information related to table 2:*

The analysis population will include all randomized participants following the intention-to-treat (ITT) principle. In case baseline information is missing, the analysis population will be following a modified intention-to-treat (mITT) principle, including only those with available baseline data for the outcome.

Continuous data with repeated measures (i.e., AUSCAN subscores) will be analyzed using linear mixed models estimating the group mean changes from baseline and the differences between groups at week 7. The analyses will include the participant as random effect, group (2 levels) and week (4 levels; week 0, 2, 4 and 7) as fixed effects, the group\*week interaction, as well as the baseline value of the outcome under analysis and the stratification factor (CMC-1 OA) as covariates. Missing data will be handled implicitly by the repeated measures mixed linear models, assuming data missing at random (MAR).

Continuous data measured only at baseline and 7 weeks will be analyzed using ANCOVA models with group as fixed effect (2 levels), as well as the baseline value of the outcome under analysis and the stratification factor (CMC-1 OA) as covariates. Missing data will be handled with multiple imputation using multivariate imputation by chained equations assuming MAR. Imputations will be conducted separately by group, and the imputation model will be conditioned on relevant variables, including baseline variables, and covariates and outcome of the analysis models. Imputation models with many auxiliary variables preserve relationships among variables and provide more precise and accurate imputations (Collins et al. 2001). Estimates will be pooled across 100 imputed datasets (Graham et al. 2007; Rubin 1987). The imputations will be performed using the *mice* package in R (van Buuren & Groothuis-Oudshoorn, 2011).

[figure not shown]
Assumptions will be checked by visual inspection of residual plots assessing the normality of residuals. In case the distributional assumptions do not hold, we will use an appropriate transformation (e.g., log-transformation in the case of right-skewed data and report the results as geometric means and geometric mean ratios), and/or, use non-parametric methods.

We will not apply explicit adjustments for multiplicity, rather we will analyze the key secondary outcomes in prioritized order (i.e. “inverse gatekeeping procedure”): The hypothesis testing of the key secondary outcomes will be performed in sequence until one of the analyses fails to show statistical significance. The hierarchy is illustrated by the order of key secondary outcomes in table 2 (top-down). For the other secondary outcomes no hypothesis testing will be done.

**Figure 2. Trajectories for the primary efficacy outcome measure (AUSCAN physical function) from baseline to 7 weeks follow-up in the ITT population**

*Hypothetical trajectories of the primary outcome measure.*

Values are least squares means over time from baseline to 7 weeks follow-up for heated mittens group (solid points) and sham mittens group (hollow points). Error bars indicate standard error of the estimates

*Further statistical information related to figure 2*

Least-squares mean estimates and standard errors for AUSCAN physical function by group will be estimated based on a model similar to that of the primary analysis.

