### Further statistical details

**Randomization:** Computer-generated randomization list was developed based upon permuted random blocks of variable size (2 to 6 in each block). The allocation ratio was 1:1 stratified for the presence of OA of the first carpometacarpal joint (CMC-1).

**Sample size:** A sample size of 200 in total will provide strong statistical power to detect a difference between groups in the primary outcome of 8 AUSCAN-function points (normalized 0-100 scale; equals 81 points on original 0-900 scale). For a two-sample pooled t-test of a normal mean difference with a two-sided significance level of 0.05 ( $P<0.05$ ), assuming a common standard deviation of 19 AUSCAN-function points (normalized 0-100 scale; equals 171 points on original 0-900 scale), a total sample size of 180 HOA patients (i.e. approximately 90 participants per group) has a power of 80.2% to detect a mean difference of 8 AUSCAN-function points (small effect size of 0.42). To account for dropouts, it was decided to include 200 patients in the trial.

**Framework:** This is a superiority trial assessing if electrically heated mittens are superior to sham mittens for improvements in physical function of the hands.

**Statistical interim analyses and stopping guidance:** None.

**Timing of final analysis:** When this statistical analysis plan was finalized and signed, recruitment to the HOT trial had not been completed. We expect recruitment to be completed by the end of March 2023. We will close the database 2 months after the last participant's last visit at the latest. Statistical analyses are expected to be completed after additionally 2 months at the latest.

**Timing of outcome assessment:** (see next section).

**Confidence intervals and P values:** All 95% confidence intervals and P-values will be two-sided.

**Multiplicity:** No explicit adjustments but hierarchical testing of primary and key secondary outcomes.

**Statistical software:** R version 4.0.3 (or newer).

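### The SAP drops a randomized participant from an outcome's analysis when that baseline value is missing; this is avoidable, costs a little precision and no bias, and needs a stated way to keep them

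*SAP*

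**What the plan says.** In section 5, the notes to Table 2 open with "The analysis population will include all randomized participants following the intention-to-treat (ITT) principle". The next sentence provides for missing baseline information: the population then becomes a modified ITT set, "including only those with available baseline data for the outcome". The rule is set per outcome and covers every row, the primary included.

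The same notes give two routes for missing data:

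- **AUSCAN subscores:** a linear mixed model with week 0 as one of four week levels. The baseline value is also a covariate. Missing data are left to the model under MAR, and no imputation is planned.
- **Outcomes measured only at baseline and week 7:** ANCOVA adjusted for baseline. "Missing data will be handled with multiple imputation using multivariate imputation by chained equations assuming MAR". The imputation model draws on baseline variables, covariates and the outcome, and is run separately by group.

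Table 2, Figure 2 and Supplementary table 1 are all titled as ITT results, and the Table 2 shell has one n per arm. Section 1 sets the sample size at 180, raised to 200: "To account for dropouts, it was decided to include 200 patients in the trial".

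**The concern.** A participant with AUSCAN observed at weeks 2, 4 and 7 but no baseline score leaves the primary analysis, although the population has just been defined as everyone randomized. No other planned analysis brings that person back. Baseline carried forward (Supplementary table 1) has no value to carry, and the per-protocol set (Supplementary table 2) requires baseline primary-outcome data.

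Three things are at stake:

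- Observed endpoint data are discarded, with some loss of precision.
- Rows of Table 2 may rest on different subsets under one ITT label and one n. The key secondary outcomes are tested in sequence, so successive tests could use different participants.
- The increase from 180 to 200 is stated to be for dropouts, not for people who were followed up.

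**Working it through.** **Inputs from the SAP (section 1, sample size).** Two-sided alpha 0.05, difference 8, 90 per group, and "assuming a common standard deviation of 19 AUSCAN-function points".

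**Assumed, because the SAP does not give them.** Fraction m of participants with a missing baseline: 1 to 10%. Baseline-to-week-7 correlation r: 0.3 to 0.7. The SD of 19 is treated as that of the quantity analysed, so that all figures stay on the SAP's own footing.

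**Step 1: the stated power.** Pooled two-sample t-test, noncentral t, 90 per group: 80.21%. The SAP's 80.2% reproduces.

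**Step 2: exclusion.** Per-group n becomes 90(1 − m), and the SE rises by the factor 1/√(1 − m). At m = 5%, n = 85.5, the factor is 1.026 and power is 78.2%.

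**Step 3: retention.** A participant with follow-up but no baseline carries a share 1 − r² of the information of a complete one (0.91 at r = 0.3, 0.51 at r = 0.7). Effective n is 90[(1 − m) + m(1 − r²)]. At m = 5%:

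- r = 0.7: 90(0.95 + 0.0255) = 87.8, power 79.2%
- r = 0.3: 90(0.95 + 0.0455) = 89.6, power 80.0%

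| Missing baseline | Power, excluded | Power, kept (r = 0.7 to 0.3) | SE ratio, excluded/kept |
|---|---|---|---|
| 1% | 79.8% | 80.0–80.2% | 1.003–1.005 |
| 2% | 79.4% | 79.8–80.1% | 1.005–1.009 |
| 5% | 78.2% | 79.2–80.0% | 1.013–1.024 |
| 10% | 75.9% | 78.2–79.9% | 1.028–1.049 |

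If all 200 have week-7 data, exclusion leaves 83.8%, 83.5%, 82.3% and 80.2% at the same four rates.

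**Step 4: check with repeated measures.** A simulated week 0/2/4/7 model with a common baseline mean gave SE ratios of 1.007–1.010, 1.016–1.024 and 1.034–1.050 at 2%, 5% and 10% missing. The average estimates with and without exclusion differed by less than 0.1 point in every setting.

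**Step 5: which way of keeping them.** Take a single-follow-up ANCOVA with baselines missing completely at random.

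- *Mean replacement.* The residual variance becomes proportional to (1 − m)(1 − r²) + m over all N. With exclusion it is (1 − r²) over N(1 − m). The two are equally precise when 1 − r² = (1 − m)/(2 − m). At m = 5% that is 0.95/1.95 = 0.487, so r ≈ 0.72. Above this, mean replacement is less precise than exclusion. In simulation the SE ratio (excluded/filled) was 0.984 at r = 0.8.
- *Multiple imputation by group.* Unbiased, with SE ratios of 1.007 to 1.021 at 5% missing for r from 0.7 to 0.3. At r = 0.7 this is less than the 1.013 of step 3, so the kept figures there are slightly favourable to imputation followed by ordinary ANCOVA.

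**The case against.** The strongest reply is that a pre-specified, openly named modified ITT set, defined by pre-treatment data, is a legitimate choice. For AUSCAN it only states what the chosen model implies. It is a contingency that may never arise: the SAP has all analysis variables checked for missing values and queried. Power stays at 80.2% even if 10% of 200 otherwise analysable patients are lost. Most of this stands, and it is why the point is minor. It does not justify the exclusion for the ANCOVA outcomes, where the planned imputation can supply the value.

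A reader might infer more than the document supports:

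- **That the planned methods already keep these people in the primary analysis.** They do not. Baseline is a covariate and AUSCAN imputation is not planned, so a further specification is needed.
- **That the primary result is biased.** Baseline is taken on days −7 to −1 before first treatment, so its absence is unlikely to depend on allocation. In simulation both approaches were centred on the true difference.
- **That the rule costs the drop from 80.2% to 78.2%.** That compares exclusion with having no missing baselines. The relevant comparison is with retention.
- **That 4.4 to 8.6% of participants would be lost through blank items.** This is 1 − 0.995⁹ to 1 − 0.99⁹. It needs an invented blank rate of 0.5 to 1% per item, independence between items, and a rule that one blank voids the nine-item total. The SAP states none of these.
- **That the ITT label conceals the exclusion.** The fallback is disclosed directly beneath Table 2.

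**Conclusion.** The point holds as a minor one. The SAP promises analysis of all randomized participants and then excludes, per outcome, those without a baseline value. This is needless for the ANCOVA outcomes, and for AUSCAN it is a consequence of the model that a small change would remove.

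The gain from retention at 180 patients is about 1 to 2 power points if 5% of baselines are missing (79.2 − 78.2 to 80.0 − 78.2) and 0.2 to 0.4 points at 1%. These sizes rest on the assumed missingness rates, correlations of 0.3 to 0.7, and missingness unrelated to allocation. If no baseline is missing, nothing changes.

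**What to change.** Before unblinding, amend the notes to Table 2:

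1. Delete the modified ITT sentence and state that participants with a missing baseline value are retained.
2. For the ANCOVA outcomes, include the missing baseline value in the planned multiple imputation.
3. For the AUSCAN outcomes, choose one of two routes and write it down. Either extend that imputation to the missing baseline, or use baseline only as the week-0 response, with a mean common to both groups and no baseline covariate.
4. Do not use single mean replacement. It can be less precise than exclusion when the correlation exceeds about 0.7. Section 3 also defines change as baseline minus follow-up, so filling only the covariate leaves the change itself undefined.
5. Report n for each row of Table 2, and keep the baseline-complete analysis as a check if any case occurs.

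The cost is a few lines of text and code.

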### **Data management:**

All outcomes: Change from baseline in all outcomes will be calculated as the baseline values minus follow-up values.

AUSCAN: The AUSCAN consists of 3 subscales, AUSCAN function, AUSCAN pain, and AUSCAN stiffness, each with 9, 5, and 1 items, respectively. Each item is scored on a 0-100 mm visual analogue scale (VAS) scale (0, best; 100, worst). Hence, the total scores of each subscale are 0-900 (AUSCAN function), 0-500 (AUSCAN pain), and 0-100 (AUSCAN stiffness).

Tender and Swollen Joint Counts: For the TJC and SJC, 15 joints in each hand are assessed: CMC-1, MCP1 to 5, IP, PIP2 to 5, and DIP2 to 5 in both hands. The scales span from 0 (no tender or swollen joints) to 30 (all joints on both hands are tender or swollen).

VAS pain: In the protocol (page 10) the description of the VAS pain outcome measurement could be read as if the VAS pain assessment was only targeted one hand. In reality, it was targeted the average of both hands and the outcome reflects the average pain intensity across both hands.

Analgesics: Use of analgesics is recorded as use of i) Acetaminophen/paracetamol, ii) NDAIDs, and iii) Other analgesics. The amount is recorded as either 'Almost daily', '2-3 times per week', 'Rarer', or 'Never'. The recording at baseline and primary endpoint is based on an interview with an investigator. In the treatment period (week 1-6) the recording is made by the participant in a diary and recorded once per week. We collapse 'Almost daily' and '2-3 times per week' into a category called 'Analgesic user' and 'Rarer' and 'Never' into the category 'Analgesic non-user'.

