### **Supplementary file 3. This SAP**

### **Supplementary table 1. Change from baseline in primary and secondary outcomes at week 7 in the ITT population, imputing missing data with BOCF**

*[same design as Table 2, but with no p-value column]*

Sensitivity analyses using the same model as in the primary analysis, but with missing data imputed using baseline observation carried forward (BOCF) technique. This assumes data missing not at random (MNAR), in contrast to the primary analysis that assumes MAR.

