### **Supplementary table 2. Change from baseline in primary and secondary outcomes at week 7 in the per-protocol population**

*[same design as Table 2, but with no p-value column]*

Subgroup analyses using the same model as in the primary analysis, but only including the per-protocol population. The per-protocol population is defined as participants who were randomly assigned to treatment, have a primary outcome data both at baseline and at the primary endpoint assessment, report mitten use of at least 15 minutes on at least 30 days, and who have no major protocol violations (see table in the supplementary file 2).

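### The primary mixed model uses the week-0 AUSCAN score as both outcome row and covariate and names no single contrast: the 5% test runs at about 7.5–9% (equal SDs and correlations), or the baseline adjustment is lost

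*SAP*

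**What the plan says.** The notes to Table 2 in section 5 of the SAP define the linear mixed model for the AUSCAN subscores, which include the primary outcome.

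- Outcome rows and random effect: "The analyses will include the participant as random effect, group (2 levels) and week (4 levels; week 0, 2, 4 and 7". Week 0 is therefore one of the four outcome levels. Participant is the only random effect, and no residual covariance structure is named.
- Covariates: "as well as the baseline value of the outcome under analysis and the stratification factor (CMC-1 OA) as covariates". The only interaction listed is group by week, so baseline has one common slope over all weeks.
- Target: "estimating the group mean changes from baseline and the differences between groups at week 7".

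Section 3 (Data management) adds: "Change from baseline in all outcomes will be calculated as the baseline values minus follow-up values".

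The model is reused. For Figure 2, means and standard errors "will be estimated based on a model similar to that of the primary analysis". Supplementary table 1 is described as "Sensitivity analyses using the same model as in the primary analysis" with baseline values carried forward, and supplementary table 2 as "Subgroup analyses using the same model as in the primary analysis" in the per-protocol population.

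**The concern.** For AUSCAN, the week-0 outcome and the baseline covariate are the same number. The target sentence mentions both changes from baseline and differences at week 7, so an analyst could take the P-value from either of two contrasts.

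- **Reading 1, adjusted group difference at week 7.** Once baseline is a covariate, the week-0 rows have almost no residual variance. They pull the common baseline slope towards 1 and the pooled variance down, so the reported standard error is too small. A change-score response does not help: the week-0 rows become exact zeros, and the week-7 estimate (apart from sign) and its standard error are unchanged.
- **Reading 2, group difference in week 7 minus week 0.** The baseline term is the same at both weeks and cancels. With complete data the result is the unadjusted difference in change scores.

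The two readings give different intervals and P-values from the same data. The model governs the primary outcome and also AUSCAN pain, the first key secondary outcome in the fixed testing sequence, so a false positive there opens the later tests. The planned residual check looks only at normality and does not target unequal variance across weeks.

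**Working it through.** **Inputs.** From the SAP, Further statistical details: "two-sided significance level of 0.05", difference 8, SD 19 (0–100 scale), 90 per group for the power statement, 200 randomized. Assumed, because the SAP does not give it: between-visit correlation r, shown from 0.3 to 0.9, with equal SDs and equal correlations unless stated.

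**The SAP's own power.** SE = 19 × √(2/90) = 2.832 and 8/2.832 = 2.825. The noncentral t with 178 df gives 80.2%, as stated.

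**Reading 1, closed form (balanced data, unit SD).**

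1. The covariate is constant within participant, so its slope is that of the participant mean on baseline: m = (1 + r + r + r)/4 = (1 + 3r)/4.
2. True residual variance at week 7: 1 + m² − 2mr.
3. Residual variance at week 0: (1 − m)².
4. The model pools the four weeks: [3(1 + m² − 2mr) + (1 − m)²]/4 = 1 − m² = 3(1 − r)(5 + 3r)/16.
5. SE ratio = √(model/true), and type I error = 2[1 − Φ(1.96 × ratio)].

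At r = 0.5: m = 0.625, true 0.7656, model 0.6094, ratio 0.892, 1.96 × 0.892 = 1.748, type I error 8.0%.

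| r | true | model | SE ratio | type I error | REML simulation |
|---|---|---|---|---|---|
| 0.3 | 0.9406 | 0.7744 | 0.907 | 7.5% | 8.1% |
| 0.5 | 0.7656 | 0.6094 | 0.892 | 8.0% | 8.5% |
| 0.7 | 0.5156 | 0.3994 | 0.880 | 8.5% | 8.7% |
| 0.9 | 0.1906 | 0.1444 | 0.870 | 8.8% | 9.3% |

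The simulations used random-intercept REML fits, 100 per arm, 10% random dropout and 6,000 null trials per row (Monte Carlo error about ±0.7 points).

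**Reading 1, unequal SDs, same r range.** If the SD falls in equal steps per visit to 0.85 of baseline, type I error is 5.8% to 7.1%. If it is 1.1 times baseline at all later visits, 7.8% to 9.0%.

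**Reading 2.** True and model variance are both 2(1 − r), so size is kept; the same simulations gave 5.7%, 5.2%, 5.1% and 5.3%. ANCOVA has variance 1 − r². The variance ratio is 2(1 − r)/(1 − r²) = 2/(1 + r): 1.33 at r = 0.5 and 1.25 at r = 0.6.

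Power with 90 per arm and difference 8, taking 19 as the SD of change, so that the ANCOVA SD is 19 × √((1 + r)/2):

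| r | reading 2 | SD under ANCOVA | power under ANCOVA |
|---|---|---|---|
| 0.5 | 80.2% | 16.45 | 90.0% |
| 0.6 | 80.2% | 16.99 | 88.1% |

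If 19 is instead the SD of a single score, the comparison is 80.2% against 90.0% (r = 0.5) and 88.1% against 94.0% (r = 0.6).

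**Separate covariance point (assumed pattern).** If correlation decays as 0.6^(weeks apart/7), reading 1 runs at 15.7% and reading 2 at 13.1%. About 10.3% remains if the week-0 rows are dropped but the random intercept is kept.

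**Repaired model.** With weeks 2, 4 and 7 as rows, unstructured REML and the same dropout (3,000 trials each, about ±0.8 points), type I error was 5.3% at r = 0.5, 5.1% at r = 0.7 and 5.5% under decay.

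**The case against.** The best defence is that the contrast is clearer than claimed. The PICOTS summary and the title of Table 2 both call the outcome change from baseline, and with week 0 as a level the natural estimate is week 7 minus week 0. Under equal SDs and correlations that reading keeps its size, and its 80.2% power is what the sample size, based on an unadjusted t-test, promised. This part stands: nothing planned is lost in power under reading 2. It does not settle the matter. Table 2 reports least squares means, section 3 defines change as a derived variable, and a change-score response leads straight back to reading 1. Under reading 2, the baseline adjustment that the SAP specifies does nothing for the primary test.

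The second defence is that the inflation depends on variances the SAP does not give. That is correct. If the SD falls in proportion to time to 0.75 of baseline, reading 1 runs at 4.3% to 6.2%; at 0.70, at 3.6% to 5.8%. These are steep falls, and the plan gives no ground for relying on them.

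Third, both estimators are unbiased under randomization. Under reading 1 the true standard error is within about 2% of ANCOVA's: √(0.9406/0.91) = 1.017 at r = 0.3. The fault is in the reported standard error, not in the estimate.

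Finally, the decay figures stem from the random intercept alone, which is a different weakness. They are fairly set apart and do not carry this finding. They bear on the fix, because dropping the week-0 rows alone would not cure that case.

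**Conclusion.** The concern holds, with high confidence, and should be resolved before unblinding. The model as written uses one measurement twice and leaves the primary contrast open. Under reading 1 the standard error is 9% to 13% too small and the two-sided 5% test runs at about 7.5% to 9%, given equal SDs and equal correlations of 0.3 or more. The excess is smaller if SDs fall moderately after baseline and can vanish if they fall steeply. Under reading 2, with equal SDs and correlations, the test is valid but has 2/(1 + r) times the variance of a baseline-adjusted analysis. The covariate cancels exactly only with complete data. Neither reading delivers the baseline-adjusted week-7 comparison that the text describes.

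**What to change.** Use only weeks 2, 4 and 7 as outcome rows, with group, week, group by week, baseline score and CMC-1 OA in the model. Alternatively, keep week 0 as an outcome row, drop the baseline covariate and constrain the two group means to be equal at week 0. In either case specify an unstructured within-participant covariance and name the group difference at week 7 as the single primary test. Apply the same model to AUSCAN pain and stiffness, Figure 2 and supplementary tables 1 and 2. A baseline-by-week term and Kenward-Roger degrees of freedom are optional.

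The cost is a sentence in the SAP and a line of model code. Under equal SDs and correlations the interval becomes about 8% to 15% wider than the too-narrow one of reading 1 (√(0.91/0.7744) = 1.08 at r = 0.3; √(0.19/0.1444) = 1.15 at r = 0.9). It is about 13% (r = 0.5) or 11% (r = 0.6) narrower than that of reading 2, from √((1 + r)/2) = 0.866 and 0.894.

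### The primary AUSCAN model states only a participant random effect, so the week-7 standard error is right only if variance and correlation are equal across visits; an unstructured covariance should be specified

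*SAP*

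**What the plan says.** The notes to Table 2 (SAP section 5) define the model for the AUSCAN subscales: "The analyses will include the participant as random effect". The fixed part has group, week (four levels, week 0 among them) and a group-by-week interaction, "as well as the baseline value of the outcome under analysis and the stratification factor (CMC-1 OA) as covariates". Its purpose is given as "estimating the group mean changes from baseline and the differences between groups at week 7". Missing AUSCAN data are left to this model under a missing-at-random assumption.

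No residual covariance structure, week-specific variance, robust standard error or degrees-of-freedom method is named there or elsewhere in the SAP. The stated diagnostic is "Assumptions will be checked by visual inspection of residual plots assessing the normality of residuals". The fallback is also about distribution: "In case the distributional assumptions do not hold, we will use an appropriate transformation", and/or non-parametric methods. The Figure 2 estimates "will be estimated based on a model similar to that of the primary analysis". The baseline-carried-forward and per-protocol analyses (Supplementary tables 1 and 2) reuse the primary model.

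**The concern.** With only a random participant effect, every visit has variance σ_b² + σ_e² and every pair of visits has covariance σ_b². The correlation between weeks 2 and 4 must then equal that between weeks 2 and 7, and week 7 must be no more variable than week 2. The standard error of the week-7 difference is built from variance components pooled over all visits.

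Week 7 is the last visit and the only one tested. If correlation fades with time, the last visit is tied less closely to the others than the pooled figure assumes, and the model claims too much precision. If variance grows, the pooled residual variance is too small for week 7. If variance shrinks, it is too large.

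At stake is the two-sided 5% level for AUSCAN function. AUSCAN pain, the first key secondary outcome in the testing order, uses the same model.

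**Working it through.** **Inputs.** From SAP section 1: SD 19 on the 0–100 scale, two-sided 5% level, 200 randomised 1:1 (100 per arm). From SAP section 2: AUSCAN at weeks 0, 2, 4 and 7. Assumed, because the SAP gives none: the correlations and any change in SD.

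**The plan's own figure.** With 90 per group, difference 8 and SD 19, the noncentrality is 8 / (19 × √(2/90)) = 2.82 on 178 degrees of freedom. The power is 80.2%, as stated. This calculation is a t-test and does not involve the correlation between visits.

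**Isolating the covariance question.** Week 0 is both a response row and a covariate in the SAP model, which is a separate problem. To keep it out, take weeks 2, 4 and 7 as responses, baseline as covariate and a random intercept. Let S be the true covariance of the four visits, with S00 the baseline variance and S77 the week-7 variance. Let c_j be the covariance of visit j with baseline, and c̄ the mean of c_j over weeks 2, 4 and 7. In large samples, per factor 2/n:

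- fitted baseline slope b = c̄ / S00
- true variance V_true = S77 − 2·b·c_7 + b²·S00
- within-person component s = mean over the three pairs of ½·Var(Y_i − Y_j)
- between-person component V_b = mean of all nine post-baseline entries of S − c̄²/S00
- variance the model reports V_model = V_b + (2/3)·s
- actual type I error = 2 × [1 − Φ(1.96 × √(V_model / V_true))]

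**Constant correlation ρ, unit variance.** V_true = 1 − ρ². V_model = (1 + 2ρ)/3 − ρ² + (2/3)(1 − ρ) = 1 − ρ². The two agree, so the error is 5.0%.

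**Strong decay, correlation 0.95^weeks, unit variance.**

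- Correlations with baseline: 0.9025, 0.8145, 0.6983. Among weeks 2, 4 and 7: 0.9025 (2–4), 0.7738 (2–7), 0.8574 (4–7).
- b = 2.4153/3 = 0.8051
- V_true = 1 − 2(0.8051)(0.6983) + 0.8051² = 0.524
- s = (0.0975 + 0.2262 + 0.1426)/3 = 0.1554
- V_b = (3 + 2 × 2.5337)/9 − 0.8051² = 0.248
- V_model = 0.248 + 0.104 = 0.352
- SE ratio = √(0.352/0.524) = 0.82; error 10.8%

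Multiplying by 19² × 2/100 gives a model SE of 1.59 against a true SE of 1.94.

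**All scenarios** (variances in points²; SD 19 unless stated; SD changes in equal steps over the four visits). The simulated column covers null trials with 100 per arm, complete data and 6,000 to 8,000 trials per scenario. The exact decay patterns varied between simulation sets.

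| Assumed truth | V_true | V_model | SE ratio | Closed form | Simulated |
|---|---|---|---|---|---|
| Constant correlation 0.7 | 184.1 | 184.1 | 1.00 | 5.0% | 4.7–5.1% |
| Mild decay (0.8 × 0.95^weeks) | 251.0 | 211.2 | 0.92 | 7.2% | 6.6–7.4% |
| Strong decay (0.95^weeks) | 189.1 | 127.0 | 0.82 | 10.8% | 9.8–11.7% |
| Constant 0.7, SD 17 rising to 21 | 225.8 | 198.4 | 0.94 | 6.6% | 6.7–7.3% |
| Constant 0.7, SD 21 falling to 17 | 148.3 | 172.6 | 1.08 | 3.4% | 3.3% |

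With SD falling from 21 to 17, simulation gave 4.6% under mild decay and 8.2% under strong decay.

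**Week 7 minus baseline, read from the four-row model.** V_true = Var(Y7 − Y0). V_model is the mean of Var(Y_i − Y_j) over all six pairs of visits.

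- Mild decay: √(0.680/0.883) = 0.88, error 8.5% (simulations about 7–8.4%)
- Strong decay: √(0.350/0.603) = 0.76, error 13.5% (one simulation 13.1%)
- Constant 0.7, SD 17 rising to 21: √(222.1/230.2) = 0.98, error 5.4%
- Constant correlation and variance: 5.0%

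**Comparator.** ANCOVA at week 7 stayed at 4.1–5.5% in every scenario. With complete data it equals an unstructured model with baseline-by-week terms.

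**The case against.** The SAP does not say that residuals are independent with a single variance. A participant effect can sit alongside a structured residual, and the analyst may intend that. A random intercept is the literal reading, but a reader who says that the plan commits itself to a wrong covariance goes further than the text. What stands is that the SAP fixes nothing else, so the primary standard error is either compound-symmetric or left open. One edit cures both.

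A reader might also infer that the primary type I error is inflated. The documents do not show this. They contain no correlations, no scenario above is anchored in trial data, and with shrinking variance the test can be conservative. The visit spacing is weak evidence: the window midpoints are days 14, 28 and 46.5, so the post-baseline gaps are 14 and 18.5 days.

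A reader who simulates the four-row model exactly as written will find larger percentages for the week-7 difference. These do not belong to this point. That model already rejects 7.3–8.7% of the time when correlation and variance are exactly constant, because week 0 is both response and covariate.

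Finally, likelihood-based handling of dropout relies on the covariance being right, but every calculation here used complete data. No size can be claimed for that effect. AUSCAN pain was not simulated separately either.

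**Conclusion.** The point holds as a conditional weakness in the specification of the primary analysis. The stated model gives a correct week-7 standard error under one covariance pattern, and the SAP neither justifies nor checks that pattern. Mild decay does modest harm. Strong decay roughly doubles the nominal 5% level, growing variance adds about two percentage points, and shrinking variance with constant correlation errs on the safe side. On the change contrast only decay matters. These sizes rest on assumed correlations and SDs, complete data and 100 per arm. They show what the wording permits, not what the trial's data will do. The case for changing it is that the remedy costs almost nothing.

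**What to change.** In the notes to Table 2, replace the random participant effect for the AUSCAN subscales with an unstructured within-participant covariance over weeks 2, 4 and 7. Use group, week, group-by-week, baseline, baseline-by-week and CMC-1 OA as fixed effects, with Kenward-Roger or Satterthwaite degrees of freedom. At minimum, keep the random effect and add a cluster-robust standard error. State that Figure 2 uses the same model; Supplementary tables 1 and 2 then follow, since they reuse the primary model.

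The cost is a change to the SAP text and the model code, six covariance parameters with about 200 participants, and possibly a slightly wider interval. The edit should be made before unblinding. It also takes week 0 out of the response, so it should be drafted together with, and cross-referenced to, the correction of the separate problem of week 0 being both response and covariate.
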